9.10. Other Potential Risks

9.10.1. Leukoencephalopathy

Leukoencephalopathy is a potential risk associated with AG-120 treatment based on clinical safety findings observed across the AG-120 clinical development program. Progressive multifocal leukoencephalopathy and posterior reversible encephalopathy syndrome (PRES), both Grade 3 SAEs, have each been reported in 1 subject.

The signs and/or symptoms of PML may begin gradually, usually worsen rapidly, and vary depending on which part of the brain is infected. Signs and symptoms may include difficulty with walking and other movements, progressive weakness, decline in mental function, visual field deficits, and speech and language disturbances. Rarely, headaches and seizures occur. Subjects should be monitored for onset of signs or symptoms suggestive of PML. Diagnostic evaluations may include consultation with a neurologist, magnetic resonance imaging (MRI) of the brain, lumbar puncture, and/or brain biopsy as clinically warranted. The Investigator should immediately contact the Study Medical Monitor when PML is a suspected or confirmed diagnosis. Treatment with AG-120/placebo should be suspended in the setting of suspected PML and permanently discontinued in subjects with confirmed PML. Subjects with a prior history of PML should not be treated with AG-120 and are excluded from this study.

Posterior reversible encephalopathy syndrome is a rare clinic-radiological neurological syndrome ([Linda and von Heijne, 2015](#)). Clinical characteristics may include subacute onset of headache, hypertension, seizures, altered mental status, visual disturbances, and occasionally other focal neurological signs. Radiologically, signs of vasogenic edema are usually seen bilaterally in the white matter of the parieto-occipital lobes, but changes can also be seen in frontal and temporal lobes, brainstem, cerebellum, and in cortical as well as deep gray matter. Subjects should be monitored for onset of neurological signs and/or symptoms that are clinically associated with PRES. Diagnostic evaluations may include consultation with a neurologist, MRI of the brain, and other recognized standard of care measures as clinically warranted. Additionally, the Investigator should consult with the Study Medical Monitor for management guidelines to be utilized in the setting of suspected or confirmed PRES.

Refer to the AG-120 IB for further details on these events.

9.10.2. Sensorimotor Neuropathy/Polyneuropathy

Sensorimotor neuropathy/polyneuropathy is a potential risk associated with AG-120 treatment based on safety findings observed across the AG-120 clinical development program. Guillain-Barre syndrome are rare, serious syndromes that affect the central and peripheral nervous systems.

Subjects should be monitored for onset of new signs or symptoms of motor and/or sensory neuropathy such as unilateral or bilateral weakness, sensory alterations, or paresthesia. If a subject experiences signs or symptoms suggestive of sensorimotor neuropathy, Guillain-Barre syndrome, or lumbosacral plexopathy, diagnostic evaluation may include a consultation with a neurologist, lumbar puncture, and electromyography. The Investigator should immediately contact the Study Medical Monitor when Guillain-Barre syndrome is a suspected or confirmed

diagnosis. AG-120/placebo should be permanently discontinued in subjects with a confirmed diagnosis of Guillain-Barre syndrome.

Refer to the AG-120 IB for further details on these events.

9.10.3. Tumor Lysis Syndrome

Tumor lysis syndrome (TLS) is a potential risk associated with AG-120 treatment based on clinical safety findings in subjects with hematologic malignancies. Refer to the AG-120 IB for further details on events of TLS.

Tumor lysis syndrome was observed in 19 (7.4%) subjects with advanced hematologic malignancies in Study AG120-C-001, 2 (3.3%) subjects with newly diagnosed AML in Study AG120-221-C-001, and 1 (4.3%) subject with newly diagnosed AML in Study AG-221-AML-005. No events of TLS have been reported in Study AG120-C-009, Studies AG120-C-002 and AG120-C-005 in solid tumors, or in clinical pharmacology studies.

Development of TLS is a known risk associated with AML. Clinical risk factors include leukocytosis (with or without disease progression) and concurrent use of cytoreductive agents, such as hydroxyurea. AG-120 can induce myeloid proliferation resulting in a rapid reduction in tumor cells, which may pose a risk for tumor lysis syndrome. In some instances, TLS events occurred in subjects who also had rising WBC counts, suggesting the possibility that these events were related to the underlying malignancy or were co-occurring with IDH differentiation syndrome. Prophylactic and treatment measures for TLS should be employed as clinically indicated.

9.11. Duration of Subject Participation

9.11.1. Treatment Duration

Daily treatment with AG-120 + azacitidine or placebo + azacitidine will begin on the first day of Cycle 1. Subjects should be treated for a minimum of six 4-week (28-day) cycles of combination therapy. With Medical Monitor approval, subjects may continue to receive:

- AG-120 or placebo following discontinuation of azacitidine, provided that they are in CR or CRi (including CRp) and need to discontinue azacitidine due to protocol-specified azacitidine-related toxicity (eg, delayed bone marrow recovery), or
- Azacitidine following discontinuation of AG-120 or placebo, provided that they have not met the definition of disease relapse or progressive disease.

Subjects should continue to receive study treatment until disease relapse, disease progression, treatment failure, development of an unacceptable toxicity (AE), confirmed pregnancy, withdrawal by subject, protocol violation, death, or End of Study.

Subjects with a response less than CR at 24 weeks or beyond can continue on treatment if demonstrating treatment benefit, defined as any of the following: 1) Transfusion-independence while on study treatment; 2) ANC >500/ μ L; or 3) platelets >50,000/ μ L.

Following discontinuation of study drug, subjects are to attend a Follow-up Visit 4 weeks (28 days) after the last dose of study drug for final assessments. When study drug is withheld from a subject in order to resolve a toxicity and the subject does not subsequently restart

treatment, EOT is defined as the date when the study drug was first held. Subjects should proceed with EOT assessments, safety assessments, and EFS/Survival Follow-up. If the decision not to restart study treatment occurs outside of the 4-week Safety Follow-up window, the subject should proceed with EFS/Survival Follow-up.

All subjects who discontinue study treatment without experiencing any 1 of the following: death, disease relapse, treatment failure, or withdrawal of consent, will be followed every Day 1 (± 7 days) of Weeks 9, 17, 25, 33, 41, 53, and every 24 weeks thereafter for EFS until they experience treatment failure, relapse, death, withdraw from the study, or until the time when 173 EFS events have occurred or as deemed necessary by the IDMC.

Once the study is unblinded, survival follow up will continue. All subjects who are alive after an EFS event will be contacted every 8 weeks for survival follow-up until death, withdrawal by subject, loss to follow-up, or when the Sponsor ends the study.

9.11.2. End of Study

At the time of primary endpoint analysis (approximately 173 EFS events or as deemed necessary by the IDMC), the study will be unblinded. Subjects on treatment at that time may continue receiving study drug. After unblinding, and if the benefit-risk profile favors treatment, subjects randomized to placebo may be offered the choice to receive AG-120. End of Study is defined as the time at which all subjects have died, discontinued the study, are lost to follow-up, or have withdrawn consent; or when the Sponsor ends the study.

9.11.3. Treatment Compliance

Subjects will be dispensed the appropriate number of Sponsor-packaged, labeled bottle(s) for 4 weeks (28 days) of dosing on Day 1 (± 3 days) of each 4-week (28-day) cycle; alternatively, subjects may be dispensed the appropriate number of bottle(s) needed until the next study visit. The subject will be asked to return all bottles and unused tablets (or empty bottles) on Day 1 (± 3 days) of each cycle or at their next study visit for assessment of compliance with the dosing regimen.

Subjects will receive instructions for home administration of study treatment along with a diary to record the date and time of each dose, as well as the number of tablets taken (see Section 9.12).

Site staff will administer all doses of azacitidine when given as study drug.

9.12. Study Drug Accountability

Accountability for the study treatment at the study site is the responsibility of the Investigator. The Investigator will ensure that the study treatment is used only in accordance with this protocol. Where allowed, the Investigator may choose to assign drug accountability responsibilities to a pharmacist or other appropriate individual.

The Investigator or delegate will maintain accurate drug accountability records indicating the drug's delivery date to the site, inventory at the site, use by each subject, and return to the Sponsor or its designee (or disposal of the drug, if approved by the Sponsor). These records will adequately document that the subjects were provided the doses as specified in the protocol and should reconcile all study treatment received from the Sponsor. Accountability records will

include dates, quantities, batch/serial numbers, expiration dates (if applicable), and subject numbers. The Sponsor or its designee will review drug accountability at the site on an ongoing basis during monitoring visits.

Study treatment must not be used for any purpose other than the present study. Study treatment that has been dispensed to a subject and returned unused must not be re-dispensed to a different subject.

Subjects will receive instructions for home administration of study treatment along with a diary to record the date and time of each dose, as well as the number of tablets taken.

All unused and used study treatment should be retained at the site until they are inventoried and verified by study site personnel and/or the study monitor. All used, unused, or expired study treatment will be returned to the Sponsor or its designee or if authorized, disposed of at the study site per the site's Standard Operating Procedures (SOPs), and documented. All material containing AG-120 and/or matched placebo will be treated and disposed of as hazardous waste in accordance with governing regulations.

9.13. Prior and Concomitant Medications and Treatments

9.13.1. Prior Medications and Procedures

All medications administered and procedures conducted within 4 weeks (28 days) prior to the first day of study drug administration (C1D1) are to be recorded in the eCRF.

As available, transfusion history, including RBC and platelet transfusion, for up to 56 days prior to C1D1 should be recorded at the Screening visit. This documentation should include dates of each transfusion and units administered.

9.13.2. Concomitant Therapy Requiring Careful Monitoring

Concomitant use of drugs with a potential for QT prolongation should be avoided and replaced with alternative treatments. If this is not possible, subjects receiving these drugs should be adequately monitored by ECG controls, drug concentration (where applicable), and serum electrolytes (ie, potassium and magnesium). See Section 9.9.1 for guidance on managing QT prolongation.

These medications include, but are not limited to:

- Fluoroquinolones, such as ciprofloxacin and moxifloxacin.
- Azole antifungals, such as fluconazole and posaconazole.
- Serotonin (5-HT₃) antagonists, such as granisetron and ondansetron.

Other examples of drugs known to prolong the QT interval are listed in Appendix 15.5.

Systemic administration of moderate or strong CYP3A4 inhibitors (see Appendix 15.7) requires careful monitoring of QTcF.

Coadministration of AG-120 with narrow therapeutic index drugs that are extensively metabolized by CYP2C9 (eg, phenytoin, warfarin) may result in decreased concentrations of these drugs. Consider alternative therapies that are not sensitive substrates of CYP2C9 during

treatment with AG-120. Subjects should be monitored for loss of therapeutic effect of these medications if coadministration with AG-120/placebo cannot be avoided. Monitor international normalized ratio (INR) levels more frequently in subjects receiving warfarin during initiation or discontinuation of AG-120/placebo.

Coadministration of AG-120 may decrease the concentrations of hormonal contraceptives. Consider alternative methods of contraception in subjects receiving AG-120/placebo. Please refer to Inclusion Criterion 10 in Section 8.2 for contraception requirements.

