9.13.3. Concomitant Therapy to be Avoided

The following therapies are contraindicated during the study while subjects are receiving study drug:

- Strong CYP3A4 inducers listed in Appendix 15.6, unless the subject can be transferred to other medications within ≥ 5 half-lives prior to dosing.
- Sensitive CYP3A4 substrate medications with narrow therapeutic windows listed in Appendix 15.6, unless the subject can be transferred to other medications within ≥ 5 half-lives prior to dosing.
- Anticancer therapy other than the treatment outlined in the protocol is not permitted while subject is receiving study treatment, with the exception of hydroxyurea as described in Section 9.13.4.3. If alternative therapy is required for treatment of the subject's disease, the subject should be discontinued from the study treatment.

The above listed medications will be allowed during the EFS and Survival Follow-up periods.

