15.6. Prohibited Concomitant Medications

Prohibited medications and certain foods are not allowed in this study (Screening Period through End of Treatment) while subjects are receiving study drug.	
Strong CYP3A Inducers	CYP3A Substrates With a Narrow Therapeutic Index
Avasimibe, carbamazepine, phenytoin, rifampin, rifabutin, St. John's wort	Alfentanil, astemizole(1), cyclosporine, dihydroergotamine, ergotamine, fentanyl, pimozide, quinidine, everolimus, sirolimus, tacrolimus, terfenadine(1)

Abbreviations: CYP = cytochrome P450.

Note that this is not an exhaustive list. For an updated list, see the following link:

<https://www.fda.gov/Drugs/DevelopmentApprovalProcess/DevelopmentResources/DrugInteractionsLabeling/ucm093664.htm>

CYP substrates with narrow therapeutic range refers to drugs whose exposure-response relationship indicates that small increases in their exposure levels by the concomitant use of CYP inhibitors may lead to serious safety concerns (eg, Torsades de Pointes).

¹ Withdrawn from the United States market because of safety reasons.

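### Protocol Section 9.13.2 gives a use-with-monitoring route for phenytoin, which Section 9.13.3, Appendix 15.6 and Exclusion Criterion 8 prohibit on study drug

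*Protocol*

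**What the plan says.** **Section 9.13.2 (careful monitoring).** The CYP2C9 paragraph says "Coadministration of AG-120 with narrow therapeutic index drugs that are extensively metabolized by CYP2C9 (eg, phenytoin, warfarin) may result in decreased concentrations". It asks sites to consider alternatives that are not sensitive CYP2C9 substrates, and continues: "Subjects should be monitored for loss of therapeutic effect of these medications if coadministration with AG-120/placebo cannot be avoided". Two other rules in the section work through appendices. For QT-prolonging drugs, which are to be avoided and replaced first and monitored only if that fails, it adds: "Other examples of drugs known to prolong the QT interval are listed in Appendix 15.5". For CYP3A4 inhibitors it says: "Systemic administration of moderate or strong CYP3A4 inhibitors (see Appendix 15.7) requires careful monitoring of QTcF".

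**Section 9.13.3 (to be avoided).** Two drug groups are contraindicated while the subject takes study drug: "Strong CYP3A4 inducers listed in Appendix 15.6, unless the subject can be transferred to other medications" and "Sensitive CYP3A4 substrate medications with narrow therapeutic windows listed in Appendix 15.6". The exception requires a switch to another drug at least 5 half-lives before dosing. The section lifts these restrictions in the EFS and Survival Follow-up periods.

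**Appendix 15.6.** The inducer column begins "Avasimibe, carbamazepine, phenytoin, rifampin, rifabutin". The substrate column begins "Alfentanil, astemizole(1), cyclosporine, dihydroergotamine, ergotamine, fentanyl, pimozide, quinidine". The listed drugs are not allowed from Screening to End of Treatment.

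**Section 8.3, Exclusion Criterion 8.** Subjects taking drugs of either group are excluded, with the same switching exception and a reference to Appendix 15.6.

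**The concern.** Adjacent sections give different instructions for the same drug. One tells the investigator what to watch if phenytoin has to be given. The other says it must not be given.

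The monitoring instruction also covers the wrong direction of the interaction. It concerns AG-120 lowering phenytoin. The ban rests on phenytoin's place among the strong CYP3A4 inducers, and Section 5.2.2.1 says such inducers could affect AG-120 PK, because AG-120 is cleared mainly by CYP3A4. A site relying on 9.13.2 has no prompt to think about AG-120 exposure.

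The exposed period is after the first dose. Section 8.4 has the Medical Monitor confirm eligibility before dosing, which should catch a subject already on phenytoin, but not an anticonvulsant started later. Such a start is conceivable: Section 9.10.1 lists seizures among the signs of two neurological conditions that it treats as potential AG-120 risks.

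**Working it through.** There is no power, alpha or sample-size figure here. The check sets the texts side by side and compares the printed lists.

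**Step 1. Status of phenytoin in each place**

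| Place | What applies to phenytoin on study drug |
|---|---|
| 9.13.2 | Named; consider alternatives; monitor for loss of its effect if unavoidable |
| 9.13.3 | Contraindicated as an Appendix 15.6 strong inducer |
| Appendix 15.6 | Named; not allowed, Screening to End of Treatment |
| Exclusion Criterion 8 | Excluded, with reference to Appendix 15.6 |

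**Step 2. Does the exception reconcile them?** No. The exception is met only by moving to another drug before dosing, so no joint use remains. The 9.13.2 fallback applies only when joint use does occur. The two cannot both hold for the same subject.

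**Step 3. Is there a tie-break?** I found no sentence ranking 9.13.2 against 9.13.3. The idea that the specific rule prevails does not settle it: 9.13.2 names phenytoin directly, while 9.13.3 reaches it through an appendix.

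**Step 4. How many drugs are in this position?** Appendix 15.6 prints 6 inducers + 12 substrates = 18 entries. Section 9.13.2 names eight drugs in its own text: ciprofloxacin, moxifloxacin, fluconazole, posaconazole, granisetron, ondansetron, phenytoin and warfarin. Only phenytoin is also among the 18.

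**Step 5. Overlap through the appendices**

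- Appendix 15.5 (47 entries) and Appendix 15.6 share 4: astemizole, pimozide, quinidine, terfenadine.
- Appendix 15.7 (13 moderate + 17 strong = 30 entries) and Appendix 15.6 share 1: cyclosporine.

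These 4 + 1 = 5 drugs differ from phenytoin. Section 9.13.2 does not name them. Its first instruction for the QT group is to avoid and replace, which agrees with the ban. Its inhibitor sentence adds a QTcF duty without granting permission. The ban can apply alongside either rule.

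**Step 6. Would plain deletion of phenytoin lose anything?** Possibly. Drugs barred by 9.13.3 become allowed again in follow-up. Section 5.2.3.1 gives a single-dose AG-120 half-life of 71 to 152 hours. Five half-lives are 5 × 71 = 355 hours (355/24 = 14.8 days) to 5 × 152 = 760 hours (760/24 = 31.7 days). The same section suggests that AG-120 induces its own metabolism, so these single-dose figures may overstate persistence after repeated dosing. Even so, AG-120 may still be present when phenytoin becomes permissible, and the CYP2C9 warning is worth keeping.

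**The case against.** The strongest reply is that phenytoin is only an illustrative example. The paragraph describes a CYP2C9 interaction, advises alternatives first, and reserves monitoring for unavoidable use. The ban is explicit in three other places, and a careful reader would follow the stricter rule. That reply is fair on likely conduct. It does not remove the conflict, because the paragraph also carries an instruction to sites, and that instruction is wrong for one of its two named drugs.

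Other safeguards exist. Table 6 has concomitant medication recorded at treatment visits, Exclusion Criterion 8 is rechecked before crossover (Section 9.6), and SAP Section 7.2 reports excluded medication as a major deviation. These make a lapse easier to notice, largely after the drug has been started. AG-120 pre-dose samples are drawn each cycle, but the protocol gives no rule for using them to manage an individual subject.

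A reader might infer more: that 6 of the 18 Appendix 15.6 drugs, a third, are both banned and permitted. The documents do not support that. For five of the six there is no permission to conflict with the ban, Appendix 15.6 marks two of them (astemizole, terfenadine) as withdrawn from the US market, and Appendices 15.5 and 15.6 describe themselves as non-exhaustive. A share of printed list entries says nothing about how often patients would be affected.

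**Conclusion.** The point stands for phenytoin: 9.13.2 is wrong as written for that drug. Its size is one named drug out of 18 printed Appendix 15.6 entries, with practical exposure mainly from phenytoin started after the first dose. The other five drugs need clarification at most.

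No effect on EFS, power or type I error should be inferred. The documents give no frequency of phenytoin use and no size for its effect on AG-120 exposure. SAP Section 5 does not list concomitant medication among the reasons for leaving the Per-Protocol Set, and the primary analysis uses all randomized subjects.

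The conclusion assumes that Appendix 15.6 states the sponsor's intent, which is reasonable because Section 9.13.3 and Exclusion Criterion 8 both rely on it. This is a low-severity inconsistency in a safety instruction that can wait for the next amendment.

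**What to change.** In Section 9.13.2:

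1. Leave warfarin as the example in the use-with-monitoring sentence and take phenytoin out of it.
2. Add: *Phenytoin is also a CYP2C9 substrate, but it is prohibited while the subject is on study drug; see Section 9.13.3 and Appendix 15.6.* This is better than bare deletion because it keeps the interaction warning for follow-up.
3. Add: *Where a drug falls under both, the prohibitions in Section 9.13.3 and Appendix 15.6 take precedence over the monitoring provisions of this section.* This also settles pimozide, quinidine, astemizole, terfenadine and cyclosporine.

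Exclusion Criterion 20, which has its own monitoring route for QT drugs, needs no edit: meeting any one criterion excludes, and Criterion 8 already covers the Appendix 15.6 drugs.

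The cost is one word removed and two sentences added at the next amendment, with no new procedure, no safeguard loosened and no change to any analysis.

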9.13.3. Concomitant Therapy to be Avoided

The following therapies are contraindicated during the study while subjects are receiving study drug:

- Strong CYP3A4 inducers listed in Appendix 15.6, unless the subject can be transferred to other medications within ≥ 5 half-lives prior to dosing.
- Sensitive CYP3A4 substrate medications with narrow therapeutic windows listed in Appendix 15.6, unless the subject can be transferred to other medications within ≥ 5 half-lives prior to dosing.
- Anticancer therapy other than the treatment outlined in the protocol is not permitted while subject is receiving study treatment, with the exception of hydroxyurea as described in Section 9.13.4.3. If alternative therapy is required for treatment of the subject's disease, the subject should be discontinued from the study treatment.

The above listed medications will be allowed during the EFS and Survival Follow-up periods.

